11.3.2.2 Secondary Outcome Measures

Efficacy of initial treatment will also be assessed with respect to the following domains:

- Craving scores – assessed by Visual Analog Scales (VAS)
- Pain – only for patients who meet criteria for chronic pain at baseline

- Pain intensity as assessed by the Brief Pain Inventory (BPI)
- Functional limitations due to pain as assessed by BPI
- Depression, assessed by the Beck Depression Inventory (BDI)
- “Quality of Life” as assessed by the SF-36.

11.3.2.3 Covariates and Predictors of Outcome

- Demographics-- age, gender, ethnicity
- Clinical characteristics:
 - pain status (no chronic pain, current chronic pain)
 - whether opioids were first used for pain treatment
 - withdrawal - assessed by Clinical Opiate Withdrawal Scale (COWS)
 - Brief Pain Inventory score at baseline
 - baseline Beck Depression Inventory score
 - prior heroin use - assessed by self-report at the baseline (Yes/no)
 - presence/absence of major depressive disorder or PTSD
 - family history of substance use disorder
 - current presence/absence of other substance use disorder in the patient

11.3.3 Statistical Considerations

11.3.3.1 Randomization

The randomization for Phase 1 will be within site and will be stratified with respect to two factors: 1) whether or not the patient has ever used heroin, and 2) whether or not the patient currently has chronic pain. Presence of ‘chronic pain’ will be operationalized by a ‘yes’ answer to the first question of the Brief Pain Inventory (whether you have pain beyond usual aches and pains) AND a duration of pain of at least three months.

11.3.3.2 Sample size

Approximately 648 subjects will enter Phase 1. Starting after the second week, they will be monitored for meeting the treatment failure criteria (see *Primary Outcome Measures* on page 11-5) (needle use would indicate failure prior to Week 2). At any time of meeting failure criteria, participants will be given the option to transition from Phase 1 to Phase 2. However, failures can elect to remain in Phase 1 through Week 12 follow-up and can transition to Phase 2 at any time up until the conclusion of Phase

1. Approximately 20% (average over EMM and SMM) are expected to be treatment successes, and about 30% are expected to drop out or refuse entry into Phase 2.

11.3.3.3 Treatment Success/Failure for Dropout and Missing Data

Dropouts in Phase 1 will be defined as the patients who voluntarily discontinue the study prior to Week 12. Subjects who discontinue the study before Week 12 will be considered treatment failures (these subjects will be eligible for Phase 2). For the patients who miss an assessment visit the self-report drug use will be obtained retrospectively; urines will not be obtained. If the patient has all data except the urines, and satisfies the criteria for success then s/he is a success, unless two or more urines are missing.

11.3.4 Hypotheses Testing

Primary Hypothesis 1.1. There will be a higher rate of treatment success among subjects receiving EMM than among patients receiving BUP/NX and SMM alone.

The following model will be used to test this hypothesis:

(1)

$$(2) \quad \text{logit}(Y_{ij}) = \beta_0 + \beta_1 \text{txt}_{ij} ,$$

where Y_{ij} is a dichotomous measure indicating whether the j^{th} patient of the i^{th} site meets the Phase 1 criteria for success or not, with $Y_{ij}=1$ for success and $Y_{ij}=0$ for failure; txt_{ij} is an indicator variable for treatments, with $\text{txt}_{ij}=1$ for EMM group and $\text{txt}_{ij}=0$ for SMM group. The model parameters will be estimated by GEE (see *Modeling of Site Effects* on page 11-4). Testing the hypothesis is equivalent to testing for significance of \hat{a}_1 .

The success rates for EMM and SMM as well as the overall success rate will be estimated with point estimate and 95% confidence intervals.

11.3.4.1 Exploratory Analyses

The following topics will be addressed in the exploratory analysis:

1. Issues related to pain:
 - a. The prevalence and characteristics of chronic pain among individuals presenting for treatment of prescription opioid dependence.
 - b. The role of pain in the addiction and treatment outcome for the study population.
 - c. The effect of treatment on pain.
2. The prevalence of various clinical characteristics of use and dependence in the study population and their role on the outcome of the standard treatment in Phase 1. In addition to pain, clinical

characteristics of interest include: use of heroin, presence of other substance use disorders, PTSD, and major depressive disorder.

3. Effect of craving and withdrawal symptoms:
 - a. Association between craving and withdrawal symptoms at baseline of Phase 1 and the primary outcome (treatment success/failure)
 - b. Effect of craving and withdrawal symptoms on time to failure
 - c. Effect of treatment on craving and withdrawal symptoms
4. The effect of treatment on quality of life measures.
5. The association between specific demographic characteristics and treatment outcome. The demographic characteristics of potential importance include: age, gender, and ethnicity.
6. The potential interaction effect of clinical and demographic characteristics on treatment outcome will also be assessed.
7. Site effect on treatment outcome, including potential interaction between treatment and site (11 d.f. test).
8. Compare time to failure in EMM and SMM.
9. Prevalence of each of the four criteria for treatment success (see *Primary Outcome Measures* on page 11-5) that were failed by treatment failures.
10. Patterns of drug use during Phase 1 among treatment failures.

11.4 Phase 2: Stabilization Treatment Study

11.4.1 Overview

Phase 2 is a stabilization treatment study for failures to initial treatment (Phase 1). Stabilization treatment consists of BUP/NX for three months plus a random assignment to SMM or EMM. The three months of treatment are followed by one month of taper and two months of follow up. The total duration of Phase 2 is six months. The primary endpoint is the end of the three months of treatment.

11.4.2 Outcome Measures and Predictors of Response

11.4.2.1 Primary Outcomes

The primary outcome measure in Phase 2 is substantial improvement at the end of the three months of treatment (yes/no). A patient has *substantial improvement* at three months if she/he is abstaining from opioids during the last week AND for at least two of the previous three weeks of the third month of BUP/NX treatment. Abstinence is determined by self-reports of opioid abstinence (missing urines will be considered positive for opioids).

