1.2.2.4 Phase 2 Study Design

All participants identified as treatment failures in Phase 1 will be offered the opportunity to be randomized to receive 12 weeks of BUP/NX stabilization treatment plus SMM or 12 weeks of BUP/NX stabilization treatment plus EMM (SMM + individual drug counseling). After the 12-week period, participants in Phase 2 will taper off of their BUP/NX dose during weeks 13-16. Taper will begin around Study Day 85 and must end by Study Day 112. During the taper period only SMM will be provided. Participants will be followed for an additional 8 weeks after the taper.

The randomization to SMM vs. EMM will be within site and will be stratified by whether participants received SMM or EMM in Phase 1.

Participants entering Phase 2 will not require induction if the time period between the end of Phase 1 and last BUP/NX dose is three days. If the period of time is four days, induction will be required prior

to entering Phase 2. This 1-day induction dose is limited to 16 mg. Follow-up for all participants will occur during Weeks 18, 20, 22 and 24 of Phase 2. As in Phase 1, the study medical clinician may adjust the BUP dose in Phase 2 at each visit in increments of up to 8mg. The maximum allowable dose is 32mg per day. Dose changes are to be determined after the study staff obtains vital signs, evaluation of illicit drug use (urine and self-report), craving, signs and symptoms of opiate withdrawal or overmedication, adverse events and current BUP/NX and other medication taken since the last visit.

Participants whose clinical status worsens during Phase 2 (e.g., increased opioid use, needle use, more dangerous behaviors such as overdoses) will be referred to other treatment options, e.g., participants will be told about methadone maintenance as well as more intensive psychosocial treatment; participants who relapse to regular opioid use in the context of severe and/or worsening pain may be referred to a pain clinic if clinically appropriate. All such participants will remain part of the study and will continue to be followed for research and safety monitoring. For coding purposes these participants will be considered treatment failures.

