7.6 Binding

This is an open-label study.

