10.2.3 Efficacy Assessments

10.2.3.1 Urine Drug Testing

Urine samples will be collected and analyzed for drugs of abuse prior to dispensing medication. All urine specimens will be analyzed by staff using drug test cups with temperature-controlled monitoring. These cups will be provided by a central supplier to all study sites. OxyImmunoassay and drug screen cards will be used to identify the following substances: oxycodone, benzodiazepines, THC, methadone, cocaine, amphetamine, methamphetamine, propoxyphene, and the Opiate 300 group analytes (morphine, heroin, and codeine). Other drugs may be detected by these analytes at high concentrations. For example, hydrocodone may be detected under the oxycodone test at high concentration levels. The cards will be provided to all study sites from a central supplier.

Urine will be collected at baseline just prior to BUP/NX induction, at each of the weekly visits thereafter, and at each follow-up visit. Urine screens for BUP will be available at Weeks 10 and 12 in Phase 1 and Weeks 22 and 24 in Phase 2. The urine screens for BUP will be used to monitor whether participants defined as "successes" at the end of Phase 1 and "substantially improved" at the end of Phase 2 (in both instances, when they are supposed to be off buprenorphine) are, in fact, taking buprenorphine that they have obtained outside the study.

The results will be recorded on the appropriate CRF.

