11.3.2 Outcome Measures and Predictors of Response

11.3.2.1 Primary Outcome Measures

The primary outcome measure is the status of treatment: success or failure. Definition of failure/success: A participant is a *Phase 1 success* if all of the following four criteria are satisfied from Week 3 to the end of Phase 1 (Week 12):

1. Use of opioids on four or fewer days per month (beginning after the end of Week 2) as evidenced by self-report.
2. Urine screen for opioids are never positive on two consecutive weeks (beginning after the end of Week 2).
3. Completion of the 4-week medication regimen and 8-week follow-up period (including Week 6 and Week 8 SMM or EMM booster visits) without participating in other formal substance abuse treatment (e.g., methadone maintenance, drug counseling, etc. Self-help groups such as Narcotics Anonymous and treatment for other issues such as medical or psychiatric problems do not count here).
4. Absence of needle use.
5. Absence of no more than one urine sample after Week 2.

A subject who fails one or more of these four criteria at any time from Week 2 to Week 12 is considered a *Phase 1 failure* and is given the option to make the transition immediately to Phase 2. Failures can elect to remain in Phase 1 through Week 12 follow-up and can make the transition to Phase 2 at any time up until the conclusion of Phase 1.

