11.4.3.3 Substantial Improvement Status for Dropout and Missing data

If a patient fails to provide a urine sample on the last week of the 12-week treatment period OR fails to provide data on two or more of the preceding three weeks, he/she will be considered NOT substantially improved (even if he/she provided negative urines on all other assessment occasions).

Definition of substantial improvement when patient discontinues the study prior to Week 12 in Phase 2. The substantial improvement status for patients who complete all 12 weeks of treatment in Phase 2 will be determined based on whether they satisfy the criteria. For patients who discontinue the study before Week 12 (due to non-compliance, being less than minimally improved after the early treatment, or dropouts) will be considered as NOT substantially improved. (Alternative definitions of substantial improvement status of dropouts will be considered to assess the sensitivity of the inferences about treatment efficacy.)

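### The Phase 2 primary outcome does not say what an observed opioid-positive urine does to a week that the participant reports as abstinent, although a missing urine counts as positive

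*Protocol*

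**What the plan says.** **The outcome.** Protocol 11.4.2.1 defines substantial improvement at three months as "abstaining from opioids during the last week AND for at least two of the previous three weeks of the third month of BUP/NX treatment". It then says how a week is judged: "Abstinence is determined by self-reports of opioid abstinence (missing urines will be considered positive for opioids"). Sections 1.2.2.3, 1.4.4, 4.1.2 and 6.1.3 use the same rule. So does the six-month secondary outcome in 11.4.2.2.

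**Missing data.** Section 11.4.3.3 covers the participant without a final sample: "If a patient fails to provide a urine sample on the last week of the 12-week treatment period", or without data in at least two of the three weeks before, "he/she will be considered NOT substantially improved (even if he/she provided negative urines on all other assessment occasions"). Those who leave the study before Week 12 are also classed as not improved.

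**Urine collection.** Under 10.2.3.1, samples are taken "at each of the weekly visits thereafter, and at each follow-up visit". A result is therefore scheduled for each of Weeks 9 to 12. In Phase 2 the urine result itself is named only as a secondary outcome (11.4.2.2, Hypothesis 2.2).

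**Phase 1, for contrast.** There a positive urine is a criterion of its own, separate from self-report: "Urine screen for opioids are never positive on two consecutive weeks (beginning after the end of Week 2") (11.3.2.1).

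**Masking.** Section 7.6: "This is an open-label study".

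**A further code.** Section 1.2.2.4 says of participants whose clinical status worsens in Phase 2: "For coding purposes these participants will be considered treatment failures". Section 8.1.2 has the same coding.

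**The concern.** The definition makes self-report decide each week and brings urine in only when it is absent. An observed positive urine has no stated effect. Followed to the letter, attending and testing positive scores better than not giving a sample. That is an odd ordering for an abstinence outcome, and it is unlikely to be what was meant.

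This is the outcome for which the 324 Phase 2 participants were chosen (11.5.1, 11.5.3). Two analysts could classify the same participant in opposite ways and both cite the protocol. If the choice is made after unmasked data exist, it may be influenced by them. Under the literal reading, the comparison also rests on what participants say while knowing their arm, although an objective result is collected each week.

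**Working it through.** **1. The two readings side by side.** Take a participant who reports no opioid use in Week 12 and is abstinent on any reading in at least two of Weeks 9 to 11.

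| Week 12 urine | Self-report decides (literal) | Self-report corroborated by urine |
|---|---|---|
| Negative | Improved | Improved |
| Positive | Improved | Not improved |
| Not provided | Not improved (11.4.3.3) | Not improved |

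Only the middle row differs, and the protocol has no sentence that settles it. The parenthesis turns a missing urine into a positive one. That has an effect only if a positive urine defeats abstinence, which the words before it do not say. The remark in 11.4.3.3 about negative urines on other occasions likewise presupposes that urine results matter.

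**2. The plan's own power figure.** Inputs: 324 participants, odds ratio 1.9, SMM rate 30% to 50%, within-site correlation 0.1 (all 11.5.3) and two-sided alpha 0.05 (11.2.1). Equal allocation, 162 per arm, is an assumption.

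- EMM rate = 1.9 × 0.30 / (0.70 + 1.9 × 0.30) = 0.57 / 1.27 = 0.449.
- Power = Φ((d − 1.96·SE0) / SE1), where d is the difference in rates, SE0 = √(2·p̄(1 − p̄)/n) and SE1 = √((p1(1 − p1) + p2(1 − p2))/n).
- With n = 162: SE0 = 0.0538 and SE1 = 0.0531, so (0.1488 − 0.1054) / 0.0531 = 0.82 and power is 79.3%.
- With randomisation within site, the variance of the contrast is multiplied by 1 − 0.1. The effective n is 162 / 0.9 = 180 and power is 83.4%.

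The stated figure of at least 80% reproduces. The sample size is not the problem.

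**3. Illustration of what denial could do under the literal reading.** The protocol gives no denial rate, so every m below is an assumption. Let m be the share of truly non-improved participants who are classed as improved on self-report. Observed rate = p + (1 − p)·m.

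*Equal denial, true rates 30% and 44.9%:*

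| m | Observed SMM | Observed EMM | Power, n = 162 | Power, correlation 0.1 |
|---|---|---|---|---|
| 0 | 30.0% | 44.9% | 79.3% | 83.4% |
| 5% | 33.5% | 47.6% | 73.8% | 78.2% |
| 10% | 37.0% | 50.4% | 68.2% | 72.8% |
| 20% | 44.0% | 55.9% | 57.3% | 61.8% |

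At m = 10% the loss is 79.3 − 68.2 = 11.1 points, or 83.4 − 72.8 = 10.6 points with the site correlation.

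*No true effect, denial differing between arms, n = 162, true rate from 50% down to 30%:*

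- A 5-point gap (0 vs 5%, or 5 vs 10%): two-sided rejection 7.3% to 10.4%.
- A 10-point gap (0 vs 10%, or 10 vs 20%): 14.7% to 26.6%.
- Example: true rate 40%, m = 10% vs 20%. Observed 0.40 + 0.60 × 0.10 = 46% and 0.40 + 0.60 × 0.20 = 52%; rejection 19% (21% with the site correlation).

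**4. A correction that lowers these figures.** Under 11.4.3.3, those who leave the study or miss the Week 12 sample are not improved whatever they report, so denial cannot reclassify them. Suppose the 15% treatment dropout in 11.4.3.2 are all such participants. The observed rate is then p + (0.85 − p)·m. The same example gives 0.40 + 0.45 × 0.10 = 44.5% and 0.40 + 0.45 × 0.20 = 49%, with rejection of about 13%. The equal-denial figure hardly moves: at m = 10% power is about 69%.

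**The case against.** The strongest reply is that nobody would run the outcome literally. The parenthesis and 11.4.3.3 both point to self-report corroborated by urine, and the protocol nowhere says that a positive urine is ignored. This stands as a statement of likely intent. It does not remove the gap, because the intended rule is not written in any of the six places where the outcome is defined. On this view 11.4.3.3 is not in conflict with a urine-based rule. It applies the parenthesis to a missing sample and is silent on an observed positive one.

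Self-report also has a fair claim to a central role. The calendar method covers each day since the last visit (10.2.3.2), while the urine panel is limited: 10.2.3.1 notes that hydrocodone may register only at high concentrations. That is a reason to keep self-report next to urine, not to disregard a positive result.

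A reader might infer that differential denial between arms is built into the design, because EMM counselors review urine results and advise abstinence. The protocol does not support that. SMM clinicians do the same at their visits (8.2.1), and SMM goes to everyone. EMM adds sessions, 18 in Phase 2 (8.2.2), so a difference in denial is possible but its direction cannot be read from the document. Masking a counseling comparison is not practicable, and the open label is not in itself a fault.

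**Conclusion.** The point holds as a defect of definition. The protocol does not say what an observed opioid-positive urine does to a week reported as abstinent, and its wording presupposes an answer that it does not give. This should be settled before data are analysed, because the two readings classify the same participant differently on the primary Phase 2 endpoint.

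Two stronger readings are not supported. One is that the protocol has decided to disregard positive urines; the text is inconsistent, and corroborated self-report may have been meant. The other is that coding worsening participants as treatment failures overrides the Week 9 to 12 data. Neither 1.2.2.4 nor 8.1.2 ties that code to substantial improvement, and 7.4.2.2 describes similar participants without it. What remains there is an ambiguity to clear up.

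The size of any bias is unknown, as is its direction. The figures of roughly 7% to 27% false positives and about 11 points of lost power rest on assumed denial rates and equal allocation. The false-positive figures also count participants whom the missing-data rule already classes as not improved. They show that the choice can matter, not that it does.

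**What to change.** In 1.2.2.3, 1.4.4, 4.1.2, 6.1.3, 11.4.2.1 and 11.4.2.2, define an abstinent week as a self-report of no opioid use **and** no opioid-positive urine in that week, with a missing scheduled urine counted as positive. Align 11.4.3.3 with this. Keep self-report alone as a sensitivity analysis.

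Section 11.4.2.2 must change together with the primary definition, because Hypothesis 2.3 models the three-month and six-month outcomes as one variable over time (11.4.4.2). Follow-up samples are taken only every other week (4.2), so the six-month definition must also say how weeks without a scheduled sample are treated. Otherwise they would all count as positive.

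Separately, state in 1.2.2.4 and 8.1.2 whether the treatment-failure code has any bearing on substantial improvement. This concerns outcome coding only and leaves referral and follow-up untouched.

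The cost is protocol wording. The weekly treatment-period urines are already collected, so no new assessment is needed. Observed improvement rates will be somewhat lower than under self-report alone.

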11.4.2.3 Covariates/Predictors of Response

- Demographics-- age, gender, ethnicity
- Clinical characteristics (at time of entry in Phase 2):
 - pain status (no pain, current pain)
 - whether opioids were first used for pain treatment
 - BPI score – only for those patients with current pain
 - prior heroin use---assessed by self-report at baseline (yes/no)
 - presence/absence of major depressive disorder or PTSD
 - family history of substance use disorder
 - current presence/absence of other substance use disorder in the patient
- Characteristics of treatment and outcome in Phase 1:
 - Treatment assignment in Phase 1
 - Time to failure in Phase 1
 - Reason for failure in Phase 1 (criteria 1-4 in *Primary Outcome Measures* on page 11-5)

- Patterns of drug use in Phase 1

11.4.3 Statistical considerations

11.4.3.1 Randomization

The randomization to SMM vs. EMM will be within site and will be stratified by whether patients received SMM or EMM in Phase 1. Block randomization will be employed.

11.4.3.2 Sample size

A total of 324 subjects will be randomized in Phase 2. Participants in Phase 2 are Phase 1 treatment failures. About 50% of patients enrolled in Phase 1 are expected to be eligible, willing, and to actually enroll in Phase 2. The treatment dropout rate in Phase 2 is expected to be lower than that in Phase 1, since participants in Phase 2 have had experience with the study and have agreed to continue, and because dropout from a stabilization dose of BUP/NX is typically lower than that from a tapering dose. In Phase 2 a rate of about 5% treatment dropout per month is expected, resulting in 15% treatment dropout during the three months of treatment and total of 30% treatment dropout for the entire study (10% treatment dropout per month is expected in Phase 1, or about 30% during the three months of Phase 1).

